### **Handling of Missing/Incomplete Medical history dates**

Medical history start dates are used to determine the duration of OA at baseline per eCRF data. Completing missing medical history dates will not imputed. Missing month will be imputed to January and missing day will be imputed to the first day of the month.

### **Handling of Adverse Events classification with missing or partial date/time of first study drug administration**

When the date and time of first study drug dose is missing, the date of randomization will be used as the start date for classification of AEs.

When the time of the first study treatment dose is missing, all AEs that occurred on the date of the first study drug dose will be considered as TEAEs.

### **Handling of missing item data for questionnaires**

#### *WOMAC*

WOMAC scores will be computed when one pain, one stiffness, or 1-3 physical function items are missing. The missing items will be imputed by the mean of available items within the same subscale. The scores will be set to missing if more items are missing.

#### *SF-36*

The Half-Scale rule will be used to impute missing item responses in the SF-36 subscale scores i.e. a score will be computed if the respondent answers at least 50% of items in that scale. The missing items in the scale will be imputed by the mean of available items rounded to the nearest whole number.

The bodily pain subscale consists of Q7 and Q8 of the instrument. Since Q7 is based on 6pt Likert score and Q8 is based on a 5pt Likert scale and because mean imputation will be meaningless, the bodily pain subscale score will not be imputed if any of the questions making up the scale is missing.

#### *EQ-5D-5L*

Index will be set to missing if any of the 5 dimensions is missing.

### **Laboratory Safety Variables below LLOQ or above ULOQ**

For central laboratory data below the lower limit of quantification (LLOQ), half of the lower limit value (i.e., LLOQ/2) will be used for quantitative analyses.

### **Missing laboratory, ECG, vital sign, physical exam, neurological exam**

No imputations for missing laboratory data, ECG data, vital sign data, physical examination, or neurological examination data will be made.

### **Handling of Potentially Clinically Significant Abnormalities**

If a patient has a missing baseline value they will be grouped in the category “normal/missing at baseline”.

For PCSAs with 2 conditions, one based on a change from baseline value and the other on a threshold value or a normal range, with the first condition being missing, the PCSA will be based only on the second condition.

For a PCSA defined on a threshold and/or a normal range, this PCSA will be derived using this threshold if the normal range is missing; e.g., for eosinophils the PCSA is  $>0.5$  GIGA/L or  $>ULN$  if  $ULN \geq 0.5$  GIGA/L. When ULN is missing, the value 0.5 should be used.

Measurements flagged as invalid by the laboratory will not be summarized or taken into account in the computation of PCSA values.

### **Date of first/last injection**

Date of first injection is the first non-missing start date of dosing filled in the ‘SC Study drug Injection’ CRF module.

If a patient’s date of the last dose is totally missing or unknown, his/her last visit date in the treatment period will be substituted.

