## 5. STUDY DESIGN

### 5.1. Study Description and Duration

This study is a randomized, double-blind, placebo- and NSAID-controlled study designed to evaluate the efficacy and safety of fasinumab in patients with OA of the knee or hip who have a history of inadequate pain relief with acetaminophen/paracetamol and a history of intolerance to or inadequate pain relief with opioids (or are unwilling to take opioids or have lack of access to opioids). The study consists of a screening period of up to 30 days, a 7 to 10 day pre-randomization/washout period (7 days with a +3 day window), a 24-week treatment period (with the last Q4W dose of study drug administered at week 20), a 20-week follow-up period, and a final phone call approximately 52 weeks after the last SC dose of study drug (Figure 1).

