#### **7.3.2. Study Drug Discontinuation**

Study drug may be temporarily or permanently discontinued due to medical need, as determined by the investigator, medical monitor, or the sponsor and according to the study stopping rules (Section 5.1.7).

Patients who permanently discontinue from study drug will be encouraged to remain in the study and to complete all study assessments. Patients who agree and thus do not withdraw from the study will be asked to return to the clinic for all remaining study visits per [Table 1](#).

Patients who permanently discontinue from study drug and who opt to withdraw from the study will be asked to complete an early termination visit (Section 8.1.3).

Patients who discontinue from study drug prior to study completion due to an AA (see Section 9.6.1.1) should return to the clinic for all remaining study visits per the visit schedule.

In the event that a patient must undergo JR surgery during the treatment or follow-up periods, he/she will be discontinued from study drug and asked to return to the study site for a pre-operative visit and for follow-up safety evaluations (as described in Section 8.2.3.10). Preoperative imaging (X-ray and MRI) will be obtained and submitted to the independent adjudication committee for review to ensure that an AA event is not in occurrence. Instructions for the submission process are provided in the study manual.

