#### 10.4.4. Safety Analysis

Safety data including TEAEs and treatment emergent AESIs, vital signs, physical examinations, laboratory tests, ECGs, and ADA formation will be listed and summarized by treatment group.

Thresholds for potentially clinically significant values in laboratory parameters and vital signs will be defined by the sponsor and be in effect at the time of final SAP approval.

The time interval to collect any AEs, including AESIs, is between the first dose of double-blinded study drug injection and the week 44 visit, as well as study drug-related SAEs occurring between the week 44 visit and the end of study.

For safety variables, 3 observation periods are defined:

- The pretreatment period is defined as the time from signing the ICF to before the first dose of study drug
- The treatment period is defined as the day of the first dose of study drug through to the day of the last dose of study drug (week 20) + 4 weeks.
- The follow-up period is defined as from the end of the on-treatment period (week 24) to the week 44 visit.

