## 5. STATISTICAL METHODS

For continuous variables, descriptive statistics will include the following: the number of patients reflected in the calculation (n), mean, median, standard deviation, minimum & maximum and 1st & 3rd quartiles (Q1 & Q3).

For categorical or ordinal data, frequencies and percentages will be displayed for each category.

**Period of Observation** - Unless otherwise stated, analysis of all safety and non-safety variables captured at multiple visits will be analyzed by the following observation periods:

- The Pre-Treatment Period is defined as the time from signing the ICF to before the first dose of study drug.
- The On-Treatment Period is defined as the time from the first dose of study drug up to 28 days after the last dose of study drug.
- The Follow-Up/Post-Treatment Period is defined from the end of the On-Treatment Period to the date of the follow-up clinic visit (Week 44 visit) or early termination date.

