### **5.6.2. Exposure to Study Drugs**

The duration of treatment exposure to fasinumab and placebo SC doses will be calculated as:

= (Date of last SC injection of study drug in the on-treatment period – date of the first SC injection of study drug administration in the on-treatment period) + 28

The duration of treatment exposure to oral study drug will be calculated as:

= (Date of last dose of oral study drug in the on-treatment period – date of first dose of oral study drug in the on-treatment period) + 1

The duration of exposure will be summarized by treatment group using descriptive statistics based on the SAF.

The number and percentage of patients exposed to study drug will be presented by specific time period for each treatment group based on the SAF. The time periods of interest are specified as:  $\geq 1$  day,  $\geq 29$  days,  $\geq 57$  days,  $\geq 85$  days,  $\geq 113$  days,  $\geq 141$  days,  $\geq 169$  days.

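### When the last injection date is totally missing, SAP 6.4 can date it at the non-dosing Week 24 visit, overstating SC exposure by 28 to 168 days

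*SAP*

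**What the plan says.** SAP 6.4, under Date of first/last injection, covers a patient whose "date of the last dose is totally missing or unknown". In that case "his/her last visit date in the treatment period will be substituted". The rule does not require the substitute to be a dosing visit or a visit with a recorded injection, and it does not cap the substitute at the date treatment was discontinued.

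The date feeds two derivations:

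- **SC exposure, SAP 5.6.2.** "The duration of treatment exposure to fasinumab and placebo SC doses will be calculated as" the last SC injection date minus the "date of the first SC injection of study drug administration in the on-treatment period) + 28".
- **On-Treatment Period, SAP Section 5.** It runs from the first dose "up to 28 days after the last dose of study drug".

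Three features of the design matter:

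- Protocol 5.1.4 runs the treatment period from Day 1 through Week 24. Protocol 5.1 describes this period "with the last Q4W dose of study drug administered at week 20", and the schedule of events (Protocol Table 1, SAP Table 2) marks no SC injection at Week 24.
- Protocol 7.3.2 keeps drug stoppers in view: "Patients who permanently discontinue from study drug will be encouraged to remain in the study and to complete all study assessments". SAP Table 2, footnote 1, says much the same.
- Protocol 7.1 and 7.3.2.1 make an exception. The 3 mg and 6 mg groups, and patients newly excluded by Amendment 4, move directly into follow-up.

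**The concern.** The last treatment-period visit records attendance, not dosing. For a completer, and for an early stopper who keeps coming to treatment-period visits, it is Week 24, when no injection is scheduled. The rule therefore dates an injection on a day when none was planned. For an early stopper it can also turn months off drug into exposure.

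For a patient who stopped all study drug early, several outputs depend on the misplaced date:

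- which adverse events count as treatment-emergent (Protocol 10.4.4.1);
- the split of all-cause joint replacements into on-treatment and post-treatment (SAP 5.8.7);
- the on-treatment laboratory and vital-sign summaries (SAP 5.8.3 and 5.8.4);
- the days from last study drug dose to first NSAID dose (SAP 5.4).

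**Working it through.** **Inputs.** First dose = Day 1. Injections are scheduled at Days 1, 29, 57, 85, 113 and 141 (baseline, then Weeks 4, 8, 12, 16 and 20). Week 24 = Day 169. Visit and dosing windows are ±7 days (Protocol Table 1 and 7.1). The formulas are those of SAP Section 5 and 5.6.2.

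**Reproducing the plan's own timeline.** Protocol 10.4.4 ends the treatment period at "the day of the last dose of study drug (week 20) + 4 weeks" and equates that with Week 24. Day 141 + 28 = Day 169, which is Week 24. The closing phone call, 52 weeks after the last SC dose, falls on Day 141 + 364 = Day 505, the scheduled Week 72 day. Both agree.

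**Longest SC exposure the schedule allows.** (141 − 1) + 28 = 168 days. With Week 20 dosed 7 days late (Day 148): (148 − 1) + 28 = 175 days.

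**Exposure under the substitution.** (169 − 1) + 28 = 196 days. With the Week 24 window (Days 162 to 176): (162 − 1) + 28 = 189, up to (176 − 1) + 28 = 203. This whole range lies above 175.

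**Size of the error**, with the substitute at Day 169:

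| True last injection | True SC exposure (days) | Substituted exposure (days) | Overstatement (days) | 28 days after true last injection | 28 days after substituted date |
|---|---|---|---|---|---|
| Baseline, Day 1 | 28 | 196 | 168 | Day 29 | Day 197 |
| Week 4, Day 29 | 56 | 196 | 140 | Day 57 | Day 197 |
| Week 8, Day 57 | 84 | 196 | 112 | Day 85 | Day 197 |
| Week 12, Day 85 | 112 | 196 | 84 | Day 113 | Day 197 |
| Week 16, Day 113 | 140 | 196 | 56 | Day 141 | Day 197 |
| Week 20, Day 141 | 168 | 196 | 28 | Day 169 | Day 197 |

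For a patient who stopped SC and oral drug together, the last two columns are the true and the derived end of the On-Treatment Period.

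**A visible symptom.** The top exposure category in SAP 5.6.2 is 169 days or more. A full course dosed exactly on schedule gives 168 days and does not reach it. A patient dosed only at baseline, with the date missing and Week 24 attended, would.

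**The case against.** **The meaning of treatment period.** Protocol 10.4.4 defines it by drug, from first dose to last dose plus 4 weeks. SAP 5.6.1 counts planned doses only until the patient leaves the treatment phase. If that were the meaning in SAP 6.4, an early stopper's substitute would fall near discontinuation, not at Week 24. This has some force: the early-stopper case does take the term as the scheduled 24 weeks. But the drug-based definition is circular when the last dose date is the unknown, and SAP 5.6.1 uses a different term. The completer error in SC exposure remains on either reading, because Protocol 10.4.4 also ends the period at Week 24.

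**Reach.** A reader might infer that everyone who stays in the study is assigned Week 24. Protocol 7.1 and 7.3.2.1 rule that out: patients moved directly to follow-up have an earlier last treatment-period visit. Joint-replacement patients follow a separate schedule.

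**The On-Treatment Period for completers.** A reader might infer that every affected patient's On-Treatment Period is wrong by 28 to 168 days. The documents do not support that. Study drug includes the oral capsules (Protocol 7.1), which are dispensed at Week 20 with accountability at Week 24. A completer's last oral dose may fall near Day 169, so an end near Day 197 is arguable. Protocol 10.4.4 points the other way. The 28-day lower bound is secure only for SC exposure.

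**Rarity.** SC doses are given at clinic visits, followed by about an hour of observation, and entered in a dedicated CRF module. A totally missing date should be uncommon. This stands.

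**Importance.** A reader might infer that the main joint-safety results are distorted. They are not. Under SAP 5.8.7, times to adjudicated arthropathy, destructive arthropathy and joint replacement start at the first dose and do not use the last dose date. SAP 5.8.1 also tabulates post-treatment and all on-study events, so a misallocated event is moved, not lost. One could add that counting more events as treatment-emergent is cautious, like the SAP's rules for missing severity and relatedness. That covers only part of the effect: the rule also inflates exposure and takes events out of the post-treatment tables.

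**Conclusion.** The point holds at minor severity. Applied as written to the 24-week schedule, the rule gives completers, and early stoppers who keep attending treatment-period visits, about 196 days of SC exposure, which no course dosed within the protocol windows can produce. The overstatement is 28 days after six doses and up to 168 days after a baseline dose only.

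For a patient who stopped all study drug early, the On-Treatment Period is extended by the same amount, and treatment-emergent status and the joint-replacement split move with it. That part assumes that the treatment period means Day 1 through Week 24. For completers the documents leave the effect on the On-Treatment Period open.

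The documents do not say how many last-injection dates will be totally missing; probably few. The likely effect on the trial's summaries is therefore small, although the error for an individual patient can be large.

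**What to change.** In SAP 6.4, replace the substitution with a rule of this kind: if the date of the last SC injection is totally missing, use the date of the last visit with a documented SC injection, taken from the SC Study Drug Injection CRF or kit accountability. The date must be no later than the Week 20 visit and not after the recorded treatment discontinuation date. Name the field that holds the discontinuation date; SAP 5.5.2 reports treatment discontinuation but does not define a date variable. State that the rule applies to the SC injection date only, and that the last oral dose date is handled separately.

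The cost is one or two sentences in the SAP and a small change to one derivation, before database lock. No new data are needed.

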## **6.5. Visit Windows**

By-visit analysis (including laboratory data, vital signs, ECG, ADA) will be summarized by the nominal visit number. Assessments taken outside of protocol allowable windows will be displayed according to the case report form (CRF) assessment recorded by the investigator. For assessments without a nominal visit number such as Unscheduled, EOT, EOS assessments, and eCOA assessments, a visit number will be assigned based on the actual visit date using the study day analysis window based on the targeted visit study day in Appendix 10.2 Schedule of Events.

The following visit windows will be used to map the unscheduled visits, early study termination visits and eCOA assessments, based on the study day:

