### **11.2. Electronic Systems**

Electronic systems that may be used to process and/or collect data in this study will include the following:

- IWRS system – randomization, study drug supply
- Rave Medidata EDC system – clinical data capture
- SAS – statistical review and analysis
- Argus - pharmacovigilance and clinical safety software system – collection and reporting of SAEs and AESIs
- Electronic Clinical Outcome Assessment systems – collect patient-reported or patient clinical assessments results

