### 5.7.1. Analysis of Primary Efficacy Variable(s)

The co-primary efficacy variables are:

1. Change in the WOMAC pain subscale scores from baseline to week 24
2. Change in the WOMAC physical function subscale score from baseline to week 24

The following hypotheses will be tested:

- $H_1$ : There is no treatment difference between fasinumab 1 mg Q4W and placebo in WOMAC pain or physical function subscale at week 24 versus there is treatment difference in WOMAC pain and physical function subscale score at week 24

For  $H_1$ , the estimand is the difference in means between the fasinumab 1 mg Q4W dose+ protocol-defined rescue medication and placebo+ protocol-defined rescue medication in the change from baseline to week 24 in the WOMAC pain and physical function scores in the FAS, regardless of whether or not rescue medication or prohibited medication had been taken. Any data collected after discontinuing treatment will not be used in the primary efficacy analysis, but used in a treatment policy sensitivity analysis.

The co-primary efficacy variables will be analyzed separately using a multiple imputation approach with a mixed-effect model for repeated measures (MMRM) based on the FAS. For patients who discontinued treatment due to lack of efficacy or AEs or deaths, their missing WOMAC subscale scores after discontinuation will be imputed with values centered at the mean baseline WOMAC subscale score of the treatment group that the patient was randomized to. For patients who discontinued treatment due to other reasons including discontinuation because of public health measures implemented in response to COVID-19, their missing WOMAC subscale scores after discontinuation will be imputed under the missing-at-random assumption using the regression method with adjustment for covariates including treatment group, randomization strata (K-L category [2 to 3, or 4], index joint [knee, hip], and geographical region [Other, Europe, North America]) and baseline WOMAC subscale score. Intermittently missing WOMAC subscale scores prior to treatment discontinuation will be imputed using the Markov Chain Monte Carlo method.

Missing data up to week 24 will be imputed 50 times to generate 50 complete data sets by using the SAS procedure PROC MI following the 3 steps below:

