#### Analysis of Treatment Policy Estimand

Sensitivity analysis of the treatment policy estimand for the co-primary endpoints will be performed using similar analysis methods as the primary efficacy analysis. The treatment policy estimand is the difference in means between each fasinumab dose+ protocol-defined rescue medication and placebo+ protocol-defined rescue medication in the change from baseline to week 24 in the WOMAC pain and physical function scores based on the FAS, regardless of study treatment discontinuation prior to week 24 and regardless of whether or not rescue medication or prohibited medication had been taken. Hence, data from all patients, including

data collected after discontinuing treatment up to week 24 will be used in this sensitivity analyses. Missing WOMAC subscale scores up to week 24 will be imputed using the same approach as in Section 5.7.1.

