#### **5.7.3. Analysis of Secondary Efficacy Variables**

The following secondary hypotheses specified in the study protocol that will be tested:

- H2: There is no treatment difference between fasinumab 1 mg Q4W and placebo in the Patient Global Assessment score at week 24 versus there is treatment difference in Patient Global Assessment score at week 24
- H3: There is no treatment difference between fasinumab 1 mg Q4W and placebo in the proportion of patients with  $\geq 30\%$  improvement in the WOMAC pain subscale

scores at week 24 versus there is treatment difference in proportion of patients with  $\geq 30\%$  improvement in WOMAC pain at week 24

- H4: There is no treatment difference between fasinumab 1 mg Q4W and NSAIDs in the WOMAC pain subscale scores at week 24 versus there is treatment difference in WOMAC pain subscale scores at week 24
- H5: There is no treatment difference between fasinumab 1 mg Q4W and NSAIDs in the WOMAC physical function subscale scores at week 24 versus there is treatment difference in WOMAC physical function subscale scores at week 24
- H6: There is no treatment difference between fasinumab 1 mg Q4W and NSAIDs in the Patient Global Assessment score at week 24 versus there is treatment difference in Patient Global Assessment score at week 24

The hypotheses H4 and H5 can be tested within the same analysis method used to test H1 as described in Section 5.7.1.

To test H2 and H6, a method analogous to that used to test H1 in Section 5.7.1 can be utilized, replacing the respective WOMAC subscale score with the PGA score. The multiple imputation algorithm will be modified to truncate values outside the range of the PGA score (0-5) in a manner similar to the primary analysis.

To test H3 the Cochran Mantel Haenszel (CMH) approach stratified by the randomization strata (K-L category [2 to 3, or 4], index joint [knee, hip], and geographical region[Other, Europe, North America]) will be used with missing data considered as non-response.

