### 6.2. Data Handling Convention for Efficacy Variables

#### 6.2.1. Data Handling Convention for Efficacy Variables due to COVID-19 Pandemic

Due to public health measures implemented to address the world-wide COVID-19 pandemic, some sites may suspend onsite study visits or patients may opt not to attend. To mitigate data loss, patients may be contacted via telephone and the results of their efficacy measures transcribed verbally and entered into the eCOA devices. For analysis purposes, this data will be treated the same as efficacy data collected in an onsite visit and will be utilized in the efficacy analyses (Bellamy 2002). Sensitivity analysis may be performed excluding data collected via telephone.

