**Table 1: Analysis Windows**

Visit Number	Visit Name	Targeted Study Daysa	Analysis Window in Study Days
1	Screen	Day -30 to Day -11	[-30, -11]
2	Pre-randomization	Day -10 to -7	[-10, -1]
3	Baseline	1	1
Phone 1	Week 2	15	[2, 22]
4	Week 4	29	[23, 43]
5	Week 8	57	[44, 71]
6	Week 12	85	[72, 99]
7	Week 16	113	[100, 127]
8	Week 20	141	[128, 155]
9	Week 24	169	[156, 196]
10	Week 28	197	[197, 267]
11	Week 44	309	[268, 407]
Phone 2	Week 72	505	≥ 408

a Study days are calculated from the first dose of study drug (Day 1).

If multiple measurements occur within the same visit window, the following rules will be used to determine the analysis value:

- When multiple valid measurements occur within the same visit window, the one closest to the target study day will be used in the analysis.
- When multiple valid measurements occur within equal distance from the target study day, the value after the target study day will be used in the analysis.

Both scheduled and unscheduled measurements will be considered for determining abnormal/PCSV values from laboratory, vital sign or ECG as well as the baseline values.

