#### 10.4. Protocol Deviations Excluding Patients from the PPS

PDID	Description of Protocol Deviation
1.05, 1.06, 1.08	Inclusion Criteria 4, 5, and 7 not met but subject randomized
2.11	Exclusion Criteria 10 met but subject randomized
3.02	Baseline visit not performed
3.16	Screening visit was not performed
5.14	WOMAC patient assessment was not administered at Week 24 Primary Endpoint Analysis
8.04	Rescue medication administered during a protocol-prohibited period prior to scheduled visit during treatment period
8.05	Use of opioid medications anytime during treatment period
8.06	Use of non-protocol specified NSAIDs any time during the treatment
F.02	Confirmed treatment unblinding (in error)

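### The Week 24 analysis window runs to day 196, so an on-time Week 28 WOMAC or PGA score can stand in for a treatment completer's missing Week 24 value

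*SAP*

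**What the plan says.** SAP 6.5 opens by saying that by-visit analyses use the nominal visit number. It then names records without one, eCOA assessments among them, and assigns those by date: "The following visit windows will be used to map the unscheduled visits, early study termination visits and eCOA assessments, based on the study day". SAP Table 1 sets Week 24 (target day 169) at days 156 to 196 and Week 28 (target day 197) at days 197 to 267. Ties within a window are settled as follows: "When multiple valid measurements occur within the same visit window, the one closest to the target study day will be used in the analysis".

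The schedules of events (Protocol Table 1, SAP Table 2) collect WOMAC and PGA at both visits, each with a window of 7 days either side of target.

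On where these scores are held, Protocol 11.2 lists electronic clinical outcome systems that "collect patient-reported or patient clinical assessments results". SAP 6.2.1 says that during COVID-19 disruption patients may be telephoned and "the results of their efficacy measures transcribed verbally and entered into the eCOA devices".

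Four other rules bear on the point:
- SAP 5.7.1, primary analysis: "Any data collected after discontinuing treatment will not be used in the primary efficacy analysis".
- SAP 5.7.1, treatment-policy analysis: "data collected after discontinuing treatment up to week 24 will be used in this sensitivity analyses".
- SAP 5.7.3, the CMH test for H3 "will be used with missing data considered as non-response".
- SAP 10.4, PDID 5.14, a reason for exclusion from the PPS: "WOMAC patient assessment was not administered at Week 24 Primary Endpoint Analysis".

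**The concern.** The Week 24 window reaches into the permitted window of the next visit, and that visit belongs to follow-up. A completer who missed Week 24 but attended Week 28 a few days early would have an off-treatment score analysed as an observed Week 24 outcome. The prespecified handling of missing data would never be triggered for that patient.

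This touches both co-primary endpoints and every key secondary endpoint. The gap since oral drug matters most for H4 to H6, because a patient in the NSAID arms would be scored three to four weeks after scheduled NSAID treatment ended. PGA against NSAIDs is also planned with only 79% power. For H3, a patient who should count as a non-responder could count as a responder.

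The scoring conditions differ too. By days 190 to 196 the opioid prohibition (Protocol 7.7.1) and the 24-hour pre-visit acetaminophen restriction (Protocol 7.2) no longer apply. The NSAID prohibition and the maximum daily acetaminophen dose still do.

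**Working it through.** **1. Allowed visit days against Table 1**

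| Visit | Allowed days | Table 1 window | Labelled as another visit |
|---|---|---|---|
| Week 24 | 169 ± 7 = 162–176 | 156–196 | 0 of 15 |
| Week 28 | 197 ± 7 = 190–204 | 197–267 | 7 of 15 (days 190–196, labelled Week 24) |

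The SAP states no rule for deriving its windows. Midpoints between adjacent targets reproduce the upper limits 22, 43, 71, 99, 127, 155 and 407. They do not reproduce Week 24 (midpoint 183, table 196) or Week 28 (midpoint 253, table 267). No reason is given for these two exceptions.

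**2. When substitution can happen**

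An on-time Week 24 score is at most 7 days from day 169. A Week 28 score on days 190–196 is 21–27 days away. The closest-to-target rule therefore always prefers the on-time Week 24 score, and substitution needs that score to be missing.

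**3. Whether another rule blocks it**

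- The primary-analysis exclusion covers data after discontinuing treatment. A completer has not discontinued.
- SAP Section 5 analyses non-safety variables by observation period, with On-Treatment ending 28 days after the last dose of study drug. It does not say which drug.
  - Counted from the scheduled last injection: 141 + 28 = 169. As a filter this would also remove compliant Week 24 visits on days 170–176 (7 of 15).
  - Counted from oral drug taken to day 168 or 169: 168 + 28 = 196, or 169 + 28 = 197. This removes none of days 190–196.

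**4. Timing of the substituted score**

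- After the scheduled last injection (day 141): 190 − 141 = 49 to 196 − 141 = 55 days.
- After scheduled oral drug ends (day 169): 190 − 169 = 21 to 196 − 169 = 27 days.
- NSAID prohibition, 16 weeks after the last injection: 141 + 112 = day 253, so still in force.

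**5. Size, under stated assumptions**

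The planned 20% dropout leaves 80% completing treatment. The other inputs are assumed:
- 2–5% of completers lack a Week 24 score.
- 25–75% of those have a Week 28 score on days 190–196 (7/15 = 47% if visits spread evenly).
- That score differs from the imputed value by 0.51–1.1 points. These are the two planned pain differences, used only as a scale.

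Results:
- Share of an arm: 0.8 × 0.02 × 0.25 = 0.4% to 0.8 × 0.05 × 0.75 = 3.0%. That is about 2–18 of 600 or 1–9 of 300.
- Shift in that arm's mean: 0.004 × 0.51 = 0.002 to 0.030 × 1.1 = 0.033 points.
- Planned SE against placebo: 2.4 × √(1/480 + 1/240) = 0.190. Ratio 0.033/0.190 = 0.17.
- Planned SE against NSAIDs, pain: 2.3 × √(2/480) = 0.148. Ratio 0.033/0.148 = 0.22.
- H3: if every substituted patient were a responder, the arm's response rate would rise by 0.4–3.0 percentage points.

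As a second scale, suppose 3% of values carry none of the treatment effect, so the planned difference is multiplied by 0.97. The plan's power figures reproduce first: 93.0% for pain against NSAIDs (stated about 92%) and 79.6% for PGA against NSAIDs (stated 79%). They fall to 91.5% and 77.2%. Power for WOMAC against placebo stays above 99%.

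**The case against.** The strongest objection is that SAP 6.5 begins with the nominal visit number and maps by date only records that lack one. The list of such records includes EOT assessments, although the schedule gives that visit a number (V9). The list might therefore mean only those eCOA records that happen to have no label. If Week 28 scores carry the V10 label, nothing is substituted. This cannot be ruled out, because the eCOA record structure is not shown. But the text names eCOA assessments as records without a visit number and then maps them without qualification, so the rule as written covers them.

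A second objection is that Protocol 7.1 counts the oral drugs as study drug, so On-Treatment could run to about day 196 or 197, close to Table 1's limit. Protocol 10.4.4, on safety variables, points the other way: it ends treatment 4 weeks after the Week 20 dose. The question is unresolved, and as step 3 shows, neither reading closes the gap.

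Some of the supporting reasons are weaker than the main point, and these objections stand:
- The H1 estimand applies whatever rescue or prohibited medication was used. The lapsed restrictions alone do not make a score unusable; the argument rests mainly on timing and time off drug.
- The treatment-policy analysis uses off-treatment data on purpose. An early stopper's score on days 190–196 raises only a timing question there.
- The PPS is meant to differ from the FAS. PDID 5.14 shows that missing Week 24 assessments are foreseen; the difference itself is not an error.
- The size inputs are assumed, and the upper figures combine the worst values in one arm only.

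**Conclusion.** The concern holds. Table 1 labels 7 of the 15 allowed Week 28 days as Week 24, and no other rule stops such a score from becoming a completer's Week 24 value in the FAS when the real one is missing. This rests on reading WOMAC and PGA as eCOA records mapped by date, which is the natural reading of the text but an inference.

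The 7 of 15 counts calendar days, not patients. The documents do not say how many patients would be affected, and the effect is likely small: at most about 0.2 of a planned standard error under the assumptions above, with partial cancellation if both arms shift alike. It would not be expected to change the placebo comparison. It should still be corrected, because it bypasses the prespecified missing-data rules for the co-primary and all key secondary endpoints, and the correction is simple.

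**What to change.** In SAP Table 1, end Week 24 at day 189 and start Week 28 at day 190. All 15 allowed days of each visit are then labelled correctly (0 of 15 mislabelled in both rows), and delayed Week 24 scores are kept up to 20 days after target. If the eCOA records do carry visit labels, SAP 6.5 should say so and state that a scheduled Week 28 score is never used as Week 24.

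The cost is two table cells before database lock. The downside is that a genuine Week 24 score taken on days 190–196, which is 14–20 days beyond the allowed window, would move to Week 28. Its Week 24 value would then be imputed, or counted as non-response for H3. Such scores should be rare, though COVID-19 disruption could produce some.

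A cut at the midpoint, day 183, also removes the overlap, but it loses late Week 24 scores on days 184–189 as well, so it is optional.
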